### **Abnormal Liver Function Test**

Investigational product will not be administered to any subject with an ALT and/or AST of  $> 3.0 \times \text{ULN}$  and concurrent elevated bilirubin  $> 2.0 \times \text{ULN}$ .

### **Other Events**

Investigational product will not be administered to a subject subsequent to an event that in the opinion of the investigator or the sponsor contraindicates further dosing or could result in complications.

#### **4.5.1.7 Reporting Product Complaints**

Any defects with the investigational product must be reported *immediately* to the MedImmune Product Complaint Department by the site with further notification to the site monitor. All defects will be communicated to MedImmune and investigated further with the Product Complaint Department. During the investigation of the product complaint, all investigational product must be stored at labeled conditions unless otherwise instructed.

MedImmune contact information for reporting product complaints:

[Redacted contact information]

#### **4.5.2 Additional Study Medications**

No other study medications are required for use in this clinical study protocol.

#### **4.5.3 Labeling**

Labels for the investigational product will be prepared in accordance with Good Manufacturing Practice (GMP) and local regulatory guidelines. The label will fulfill GMP Annex 13 requirements for labeling. Label text will be translated into local languages, as required.

#### **4.5.4 Storage**

[REDACTED]

#### **4.5.5 Treatment Compliance**

Investigational product is administered by study site personnel, who will monitor compliance. The administration of all investigational product should be recorded in the appropriate sections of the eCRF.

#### **4.5.6 Accountability**

The investigator's or site's designated investigational product manager is required to maintain accurate investigational product accountability records. Upon completion of the study, copies of investigational product accountability records will be returned to MedImmune. All unused investigational product will be returned to a MedImmune-authorized depot or disposed of upon authorization by MedImmune.

It is the investigator/institution's responsibility to establish a system for handling investigational product to ensure that:

- Deliveries of investigational product from the sponsor are correctly received by a responsible person (eg, a pharmacist)
- Such deliveries are recorded
- Investigational product supplies are handled and stored safely and properly
- Investigational product is only dispensed to subjects in accordance with this protocol

- Any unused investigational product is accounted for and returned to designated facility or the sponsor for destruction upon authorization by the sponsor. Certificates of destruction should be signed and filed.

At the end of the study, it must be possible to reconcile delivery records with records of usage and returned stocks. Any discrepancies must be accounted for. Certificates of delivery and return must be signed, preferably by the investigator or a pharmacist.

## **4.6 Treatment Assignment and Blinding**

### **4.6.1 Methods for Assigning Treatment Groups**

For the double-blind induction and maintenance periods of the study, an IVRS/IWRS will be used to randomize subjects to a treatment arm, assign a unique randomization code, and assign investigational product kit numbers. A total of approximately 342 subjects will be randomized into 1 of 5 treatment groups:

- Treatment Group 1: MEDI2070 – high (76 subjects)
- Treatment Group 2: MEDI2070 – high-medium (76 subjects)
- Treatment Group 3: MEDI2070 – low-medium (76 subjects)
- Treatment Group 4: MEDI2070 – low (38 subjects)
- Treatment Group 5: Placebo (76 subjects)

Subjects will be stratified based on the number of prior anti-TNF $\alpha$  agents that failed or were not tolerated (1 vs > 1). The randomization will be based on permutation block algorithm. The maximum number of subjects within each stratum will not be set a priori.

During the 24-week, open-label period of the study, all subjects will receive 210 mg SC MEDI2070.

A subject is considered randomized into the study when the investigator notifies the IVRS/IWRS that the subject meets eligibility criteria and the IVRS/IWRS provides the assignment of blinded investigational product kit numbers to the subject.

Investigational product (MEDI2070 or placebo) must be administered the same day the investigational product is assigned. If there is a delay in the administration of investigational product such that it will not be administered within the specified timeframe, the study monitor must be notified immediately.

## **4.6.2 Methods for Ensuring Blinding**

This study includes double-blind induction and maintenance periods. Neither the subject nor any of the investigator or sponsor staff who are involved in the treatment or clinical evaluation of the subjects will be aware of the treatment received (International Conference on Harmonisation [ICH] E9; see Section 4.6.3.2 for unblinding related to planned analysis). Since MEDI2070 and placebo can be distinguished, investigational product will be handled by an unblinded investigational product manager and handed over to qualified site staff who will administer the investigational product to subjects. An independent investigational product monitor will also be unblinded to perform investigational product accountability. In the event that the treatment allocation for a subject becomes known to the investigator or other study staff involved in the management of study subjects, the sponsor must be notified immediately. If the treatment allocation for a subject needs to be known to treat an individual subject for an AE, the investigator must notify the sponsor immediately and, if possible, before unblinding the treatment allocation.

## **4.6.3 Methods for Unblinding**

### **4.6.3.1 Unblinding in the Event of a Medical Emergency**

In the event of a medical emergency, the investigator may unblind an individual subject's investigational product allocation. Instructions for unblinding an individual subject's investigational product allocation are contained in the IVRS/IWRS manual. In general, unblinding should only occur if management of the medical emergency would be different based on the subject having received investigational product. In the majority of cases, the management of a medical emergency would be the same whether or not investigational product was received by the subject. If this was the case, the investigational product allocation should not be unblinded.

MedImmune retains the right to unblind the treatment allocation for TESAEs that are unexpected and are suspected to be causally related to an investigational product and that potentially require expedited reporting to regulatory authorities.

If a subject's investigational product allocation is unblinded prior to that subject having completed the Week 28 visit and all its associated assessments, the subject should be discontinued from investigational product.

### **4.6.3.2 Unblinding for Planned Analysis Purposes**

An interim analysis may be performed, as described in in Section 4.8.10. The analysis would be conducted by a limited number of sponsor personnel who are not involved in the conduct

of the study. The study site personnel and sponsor personnel directly associated with the conduct of this study and the study subjects will remain blinded to the subject-specific treatment assignment and to the outcome of interim analysis until the completion of the 28-week placebo-controlled, double-blind period. No changes to the conduct of this study or data analysis are planned based on the interim analysis.

The primary analysis will be performed when all subjects complete the initial 16-week, induction period. A further analysis is planned when all subjects complete the 28-week, maintenance period. At the time of the primary analysis, selected personnel from the sponsor will be unblinded to individual treatment assignments as will be outlined in an unblinding plan. The MedImmune clinical team, study subjects, site monitors, and investigators will remain blinded to subject-specific treatment assignments. The study will be formally unblinded when the last subject reaches the end of the maintenance period.

#### **4.7 Restrictions During the Study and Concomitant Treatment(s)**

The investigator must be informed as soon as possible about any medication taken from the time of screening until the end of the clinical phase of the study (final study visit). Any concomitant medication(s), including herbal preparations, taken during the study will be recorded in the eCRF.

##### **4.7.1 Permitted Concomitant Medications**

Investigators may prescribe concomitant medications or treatments deemed necessary to provide adequate supportive care except for those medications identified as “excluded” as listed in Section 4.7.2. Specifically, subjects should receive full supportive care during the study, including transfusions of blood and blood products, and treatment with antibiotics, anti-emetics, antidiarrheals, and analgesics, and other care as deemed appropriate, and in accordance with their institutional guidelines.

In addition, the following concomitant medications for CD are permitted during the study:

- 5-aminosalicylates, only if being taken at baseline
- Prednisone up to 20 mg/day or equivalent, only if being taken at baseline
- Budesonide up to 9 mg/day, only if being taken at baseline
- Azathioprine, only if being taken at baseline
- 6-mercaptopurine, only if being taken at baseline
- Methotrexate, only if being taken at baseline

- Oral antibiotics for CD (except for the treatment of acute illness), only if being taken at baseline
- Probiotics (eg, Culturelle and *Saccharomyces boulardii*), only if being taken at baseline
- Antidiarrheals (eg, loperamide and diphenoxylate with atropine) for control of chronic diarrhea, only if being taken at baseline

The investigator may not increase the subject's dose of the permitted concomitant medications listed above, and may not initiate treatment with any of these medications after the deadlines specified in the inclusion criteria, Section 4.1.2, criterion #6.

The dose of the medications listed above may not be reduced during the subject's study participation before the Week 16 assessments, including ileocolonoscopy, have been completed, with the exception that antidiarrheal agents may be stopped if the subject has had no stools in 3 consecutive days. After any such stopping of antidiarrheal agents during the double-blind period, if any recurrence of loose stools occurs prior to Week 8, antidiarrheal use should be immediately resumed.

Subjects receiving oral corticosteroids should initiate oral corticosteroid tapering as per local standard of care if, after Week 16, they have achieved both:

- SES-CD response (see Section 2.2), AND
- PRO2 response (see Section 2.2)

For assessment of the SES-CD score for the purpose of tapering oral corticosteroid therapy, the investigators' own scoring of these results may be used in place of central scoring.

In the event that the dose of any of the medications listed above must be reduced for the subject's safety, investigational product must be withdrawn and an early termination visit must be completed.

Background CD medication is not regarded as investigational product, and will not be provided by the sponsor.

#### **4.7.2 Prohibited Concomitant Medications**

Subjects must be instructed not to take any medications, including over-the-counter products, without first consulting with the investigator.

The following medications or interventions are considered exclusionary and are not permitted as specified below through Week 52 of the study. The sponsor must be notified if a subject receives any of these during the study:

- Natalizumab (Tysabri®)
- Anti-TNF $\alpha$  agents
- Vedolizumab
- Any commercially available or experimental biologic agent, eg, ustekinumab
- Calcineurin inhibitors eg, cyclosporine (Neoral®) and tacrolimus (FK 506/Prograf®)
- Mycophenolate mofetil (CellCept®)
- Sirolimus (rapamycin)
- IV or intramuscular steroids
- Topical (rectal) aminosalicylic acid (eg, mesalamine) or topical (rectal) steroids
- Thalidomide
- Live attenuated vaccine
- Intra-abdominal surgery
- Elemental diet
- Any experimental product or device as specified in Section 4.1.3 (exclusion criterion #31)

In the event that a subject receives a treatment/intervention listed above, investigational product must be withdrawn and an Early Termination Visit must be completed (see Early Termination visit, Section 4.2.3).

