**INVESTIGATIONAL PRODUCT, DOSAGE, AND MODE OF ADMINISTRATION**

Subjects will receive investigational product (MEDI2070 or placebo) by IV infusion and/or SC injection at Week 0 (Day 1) then once Q4W during the 16-week, double-blind, placebo-controlled, induction period (ie, Weeks 4, 8, and 12) and the 12-week, double-blind, placebo-controlled, maintenance period (ie, Weeks 16, 20, and 24). All subjects who complete the double-blind, maintenance period will have the option to enter the 24-week, open-label period. All subjects entering the open-label period will receive open-label MEDI2070 (210 mg SC) once Q4W (ie, Weeks 28, 32, 36, 40, 44, and 48).

A total of approximately 342 subjects will be randomly assigned to 1 of 5 treatment groups:

Treatment Group	Double-blind Period				Open-label Period
	Induction			Maintenance	
	Week 0	Week 4	Weeks 8 and 12	Weeks 16, 20, and 24	Weeks 28, 32, 36, 40, 44, and 48
1 - High (n = 76)	700 mg MEDI2070 IV + placebo SC	700 mg MEDI2070 IV + placebo SC	210 mg MEDI2070 SC	210 mg MEDI2070 SC	210 mg MEDI2070 SC
2 - High-medium (n = 76)	280 mg MEDI2070 IV + placebo SC	210 mg MEDI2070 SC + placebo IV	210 mg MEDI2070 SC	210 mg MEDI2070 SC	210 mg MEDI2070 SC
3 - Low-medium (n = 76)	210 mg MEDI2070 SC + placebo IV	105 mg MEDI2070 SC + placebo IV	105 mg MEDI2070 SC	105 mg MEDI2070 SC	210 mg MEDI2070 SC
4 - Low (n = 38)	70 mg MEDI2070 SC + placebo IV	35 mg MEDI2070 SC + placebo IV	35 mg MEDI2070 SC	35 mg MEDI2070 SC	210 mg MEDI2070 SC
5 - Placebo (n = 76)	Placebo SC and IV	Placebo SC and IV	Placebo SC	Placebo SC	210 mg MEDI2070 SC

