### **1.5.1 Benefit-risk Assessment**

Results from previous clinical studies have provided safety and tolerability data for MEDI2070 and shown significantly greater efficacy for MEDI2070 compared with placebo for achieving CDAI response, CDAI 100-point improvement, and decreases in C-reactive protein (CRP) and fecal calprotectin (Study CD-IA-MEDI2070-1147). No safety risk of MEDI2070 was identified. In Study CD-IA-MEDI2070-1147, TEAEs, TEAEs of  $\geq$  Grade 3 severity, TESAEs and TEAEs leading to discontinuation of investigational product occurred in equivalent numbers of subjects in the placebo and MEDI2070 groups. TEAEs related to investigational product and adverse events of special interest (AESIs), including infections, were more common in the placebo group. The combination of observed efficacy and apparent safety in the Phase 2a study (CD-IA-MEDI2070-1147) suggests an acceptable benefit-risk balance to justify exposing approximately 5-fold more subjects with moderate to severe CD to the range of doses planned in this study.

Although no safety risks for MEDI2070 have been identified, the immunoregulatory role of IL-23 in humans is not completely understood. Potential risks include infections, malignancies, complications associated with vaccination, infusion reactions, injection-site reactions, hypersensitivity, immune complex disease, and neurological and visual toxicities. Subjects will be closely monitored during the study with regular full blood analysis including differential white cell count and serum chemistry to monitor the risk of infection. Visual acuity tests, ophthalmoscopy, and complete physical and neurologic examinations will be performed at screening and during the study. In addition, live/attenuated vaccinations will not be permitted during the study. Exclusion criteria have been formulated to ensure that subjects at increased potential risk due to the mechanism of action of MEDI2070 are not enrolled in the study.

In addition, an independent Data Monitoring Committee (DMC) will monitor and protect the safety of the subjects through review of safety data on a regular basis throughout the double-blind period of the study; ie, until the last subject completes Week 28 (see Section 4.8.9).

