## 3 STUDY DESIGN

### 3.1 Description of the Study

#### 3.1.1 Overview

This is a 3-part Phase 2b study (Figure 3.1.1-1) comprising a 16-week, double-blind, placebo-controlled, induction period; a 12-week, double-blind, placebo-controlled, maintenance period; and a 24-week, open-label period designed to evaluate the short-term efficacy and the short- and long-term safety of MEDI2070 in subjects with moderate to severe, active CD who have failed or are intolerant to anti-TNF $\alpha$  therapy as determined by the investigator. Subjects will be stratified based on the number of prior anti-TNF $\alpha$  agents that failed or were not tolerated (1 vs > 1).

[figure not shown]
Approximately 342 subjects at approximately 300 centers worldwide will be randomly assigned to 1 of 5 treatment groups to receive IV and SC investigational product (MEDI2070 or placebo) once Q4W during the double-blind, placebo-controlled, induction and maintenance periods. Subjects who complete the double-blind, placebo-controlled, maintenance period (Week 28) will have the option to enter a 24-week, open-label period in which they will receive open-label MEDI2070 (210 mg SC) Q4W (Weeks 28 through 48).

All subjects will be followed for safety at 3 visits over 28 weeks (Weeks 60, 70, and 80 for subjects completing the open-label period) after their last dose of investigational product.

An interim analysis may be conducted when at least 75% of the total planned number of subjects has completed the Week 16 Visit or withdrawn prior to the Week 16 Visit. The study site personnel and sponsor personnel who are directly associated with the conduct of

this study and the study subjects would remain blinded to the subject-specific treatment assignment as well as the results of this analysis until the completion of the double-blind, maintenance period. No changes to the conduct of this study or data analysis are planned based on the interim analysis.

The primary analysis will be performed when all subjects complete the initial 16-week, induction period. A further analysis is planned when all subjects complete the 28-week, randomized, placebo-controlled, double-blind period. The final analysis, including all study periods and all data, will be performed at the end of the study.

Subjects will be randomized to 1 of 5 treatment groups using a [REDACTED] formulation of MEDI2070 (Table 3.1.2-1).

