#### **4.1.6 Discontinuation of Investigational Product**

An individual subject will not receive any further investigational product if any of the following occur in the subject in question:

1. Withdrawal of consent from further treatment with investigational product or lost to follow-up
2. An AE that, in the opinion of the investigator or the sponsor, contraindicates further dosing
3. Subject has had, or requires intra-abdominal surgery
4. Pregnancy (see Section 5.6.4) or intention to become pregnant
5. Subject receives any live vaccine
6. Severe noncompliance to this study protocol, as determined by the investigator or medical monitor
7. Recurrence of significant CD symptoms, that warrants escalation in therapy, according to investigator judgment, at any time during the study
8. Subject develops a malignant neoplasm
9. Mycobacterial infections, systemic fungal infections, or viral infections requiring hospitalization or parenteral antiviral therapy
10. Failure to receive a scheduled dose of investigational product within the dosing window during the double-blind periods of the study (Section 3.1.2)
11. Failure to receive 2 consecutive scheduled doses of investigational product within the dosing window during the open-label period of the study (Section 3.1.2)

Subjects who are permanently discontinued from further receipt of investigational product, regardless of the reason (withdrawal of consent, due to an AE, other), will be identified as

having permanently discontinued treatment. Subjects who permanently discontinue treatment may either be considered to have completed the study or not to have completed the study.

Subjects who are permanently discontinued from receiving investigational product will be followed for safety for 28 weeks after the last dose of investigational product, including the collection of any protocol specified blood, urine, or fecal specimens, unless consent is withdrawn or the subject is lost to follow-up or enrolled in another clinical study. In addition, subjects who are permanently discontinued from further receipt of investigational product will be referred for appropriate medical care by the investigator, as required. Such referral will be taken in coordination with the subjects' personal physician.

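### The live-vaccine ban in Section 4.7.2 stops at Week 52, 4 weeks after the last open-label dose, and is narrower than, or at best ambiguous against, the mitigation stated in Section 1.5.1

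*Combined protocol and SAP*

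**What the plan says.** **The operative rule.** Section 4.7.1 of the protocol reads "Investigators may prescribe concomitant medications or treatments deemed necessary to provide adequate supportive care except for those medications identified as" excluded, and points to Section 4.7.2 for the list. Section 4.7.2 opens its list with "The following medications or interventions are considered exclusionary and are not permitted as specified below through Week 52 of the study". Live attenuated vaccine is one of the items and has no duration of its own. The next sentence sets no week limit: "The sponsor must be notified if a subject receives any of these during the study".

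**The stated mitigation.** Section 1.5.1 includes "complications associated with vaccination" among the potential risks and answers that "live/attenuated vaccinations will not be permitted during the study". Exclusion criterion 24 (Section 4.1.3) also turns away anyone planning a live vaccine at any point over the course of the study.

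**Dosing and follow-up.** Subjects entering the open-label period receive "open-label MEDI2070 (210 mg SC) once Q4W (ie, Weeks 28, 32, 36, 40, 44, and 48"). Section 3.1.1 states: "All subjects will be followed for safety at 3 visits over 28 weeks (Weeks 60, 70, and 80 for subjects completing the open-label period"). Under Section 4.1.6, subjects who stop treatment early "will be followed for safety for 28 weeks after the last dose of investigational product".

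**The concern.** The benefit-risk section names a hazard and presents a ban as the protection against it. An investigator deciding on a vaccination will look in Section 4.7.2, and after Week 52 that section contains no ban. A site following it literally could give a live vaccine from Week 53, which is 53 − 48 = 5 weeks after an antibody dose and still within safety follow-up.

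The other provisions in the readable text do not close the gap:

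- Notifying the sponsor and consulting the investigator before taking any medication (both in 4.7.2) would bring a vaccination to light. They do not forbid it.
- Adverse event collection to the end of participation (5.4.1) records consequences.
- Criterion 24 acts at entry and concerns plans held then.
- Receiving a live vaccine stops further investigational product (4.1.6, and again in 4.7.2). After Week 48 there is no dose left to stop.

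What is at stake is subject safety and the consistency of a safety instruction. No efficacy or safety analysis depends on it.

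**Working it through.** The plan gives no figure of its own to reproduce, so the check is week arithmetic followed by a comparison of wording.

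**Inputs.** Ban ends at Week 52 (4.7.2). Last double-blind dose at Week 24 and open-label doses at Weeks 28 to 48 every 4 weeks (synopsis, dosage section). Last safety visit for completers at Week 80 (3.1.1). Follow-up of 28 weeks after the last dose for those who stop early (4.1.6).

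**Completers, to the scheduled last visit.**

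- Follow-up after the last dose: 80 − 48 = 32 weeks.
- Covered by the ban: 52 − 48 = 4 weeks.
- Not covered: 80 − 52 = 28 weeks.

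**Completers, on the 28-week basis.** 48 + 28 = Week 76, and 76 − 52 = 24 weeks not covered. The two answers differ because the Week 80 visit falls 28 weeks after Week 52, not 28 weeks after the Week 48 dose.

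**Others, uncovered weeks = (last dose week + 28) − 52.**

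| Last dose (week) | 28-week follow-up ends (week) | Weeks outside the ban |
|---|---|---|
| 24 | 52 | 0 |
| 28 | 56 | 4 |
| 32 | 60 | 8 |
| 36 | 64 | 12 |
| 40 | 68 | 16 |
| 44 | 72 | 20 |

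Week 52 thus fits a subject whose last dose is the final double-blind dose exactly. The gap appears only once a subject is dosed in the open-label period.

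**How far does *during the study* reach?**

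| Points to the final visit | Points to Week 52 or the treatment period |
|---|---|
| 4.7: medications are recorded up to the final study visit | 6.3.1: an open-label subject counts as having completed the study if followed to the end of Week 52 |
| 6.3.3: the study ends at the last protocol-specified visit of the last subject | 5.6.4.2: male subjects are restricted during the study and, as an added period, for 26 weeks after the last dose |
| 3.1.1: safety visits at Weeks 60, 70 and 80 | |
| 4.7.2: uses a Week 52 limit and *during the study* in adjacent sentences, as different terms | |

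The left column is the more natural reading. Section 6.3.1 assigns a completion status, and it also counts a subject who refuses all follow-up visits as not having completed. The right column still keeps the other reading open.

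**Other post-dose windows.** Safety follow-up after early stopping is 28 weeks (4.1.6). Open-label adverse events count as treatment-emergent up to 28 weeks after the last dose (Section 3.8.1.3 of the SAP written after early termination; Section 3.9.1.3 of the full SAP). The male contraception period is 26 weeks (5.6.4.2). After a Week 48 dose these end at Week 76, Week 76 and Week 48 + 26 = Week 74. The vaccine ban ends at Week 52.

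**The case against.** The strongest reply is that there are not two competing rules. Section 1.5.1 is a one-line summary in the Introduction, while Section 4.7.2 is the rule sites apply, and it supplies the duration. Week 52 is one full dosing interval after the Week 48 dose. The stated consequence of a breach, product withdrawal and an Early Termination Visit, makes sense only around dosing. On this view *during the study* means the treatment period, as 6.3.1 and 5.6.4.2 suggest, and changing 1.5.1 to say Week 52 would settle the wording equally well.

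Much of this stands. A reader might infer that the protocol flatly contradicts itself. The documents do not support that, because the phrase is undefined and a Week 52 reading is available. A reader might also infer that 4 weeks is clinically too short. That cannot be shown: the half-life is not visible, and the 26- and 28-week windows show what the plan does elsewhere, not how long the drug persists. Nor can one say that no vaccine rule exists after Week 52 anywhere in the protocol. Section 4.2.3, which covers early termination and safety follow-up, is not readable, and parts of the eligibility criteria are blacked out.

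What does not stand is that nothing needs doing. On the shorter reading, the benefit-risk section still describes its protection in words that a reader will most naturally take as longer. A safety restriction should not depend on which section a site consults. Aligning 1.5.1 downward would remove the ambiguity but would keep the 4-week window, for which the readable text gives no reason.

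**Conclusion.** The point holds as a minor, safety-only improvement. The operative ban is narrower than the stated mitigation on the more natural reading, and ambiguous against it on the other.

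The size is in calendar weeks: 28 for open-label completers to the Week 80 visit, 24 on the 28-week basis, 4 to 20 for those last dosed at Weeks 28 to 44, and none for those last dosed at Week 24 or earlier. No number of subjects or events is estimated. The SAP Introduction records 29 subjects randomized before termination, so few people could have been reached.

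The conclusion assumes that the redacted text holds no further vaccine rule. It covers live vaccines only and makes no claim about the clinical size of the risk.

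**What to change.** Take live attenuated vaccine out of the Week 52 limit in Section 4.7.2 and give it its own sentence: *Live attenuated vaccines are not permitted from Day 1 through the subject's final safety follow-up visit, at least 28 weeks after the last dose.* Use the same wording in Section 1.5.1. Leave Week 52 in place for the other listed items. This matches the safety follow-up and treatment-emergent adverse event windows. Before making the edit, check Section 4.2.3 for an existing rule.

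The cost is one list item moved, one sentence added and matching words in the Introduction. No new data are needed, because medications are already recorded to the final visit. The downside is that completers defer live vaccines by up to 80 − 52 = 28 weeks. Because the study is closed (SAP Appendix 6.3), the practical value lies in correcting the text before it is reused in a later protocol.
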